### **10.4. Treatment Compliance**

Each dose of dalantercept or placebo will be administered by SC injection(s) at the clinical site by the study staff and will be documented in the study record.

Daily dosing of axitinib will be the responsibility of each patient. Drug accountability will be performed at each study visit by the study staff and recorded in the patient's study record.

### **10.5. Treatments Administered**

Patients will be enrolled and will receive dalantercept or placebo on study day 1 of each 3 week cycle, with safety follow-up visits as outlined in the Schedule of Events ([Section 2](#)). Patients should be observed for a minimum of 30 minutes following treatment with dalantercept or placebo.

Patients will receive continuous dosing of axitinib at a starting dose of 5 mg PO BID, as per prescribing information (see Inlyta® [axitinib] prescribing information, *Dosage and Administration*).

Patients may be discontinued from treatment for reasons outlined in [Section 9.4](#).

## 10.6. Dose Modifications and Delays

### 10.6.1. Dose Modifications of dalantercept

Patients will continue to receive the same dose level of dalantercept or placebo as they were assigned at study entry unless a dose modification is required. In general dose delays for reasons other than management of AEs are discouraged. A dose delay of up to 3 weeks for dalantercept/placebo will be allowed at the discretion of the investigator in consultation with the medical monitor for reasons including management of AEs and for mitigating circumstances (e.g. planned procedures and patient request). Palliative radiation to pre-existing non-target lesions per RECIST v1.1 that have not demonstrated unequivocal radiographic progression will be allowed provided dalantercept/placebo dosing does not occur within 1 week pre- and post-radiation completion. Axitinib should be held 2 days before and resumed 2 days after completion of radiation. If administration of dalantercept/placebo cannot be resumed within 3 weeks after the scheduled start of the next treatment cycle, the patient should be discontinued from the study and should complete the final visit. Exemptions may be considered for those patients who are determined by the investigator to have received clinical benefit from treatment. If a dose is delayed, the patient should resume the study at the planned dosing cycle (e.g. if the patient missed a dose at C4D1, then they would resume dosing at C4D1 and not skip to C5D1).

Patients who experience dalantercept/placebo related AEs may continue treatment with dalantercept/placebo, provided that the AE can be managed (see below).

[Table 3](#) describes the management of related AEs and required dose modifications for dalantercept/placebo. For any AE, including AEs not specifically mentioned in the table below, the investigator may decide to delay dosing or modify the dose level of dalantercept/placebo based on their clinical judgment. If possible, these decisions should be discussed with the medical monitor prior to implementation. If more than 1 AE occurs that would require a dose modification, upon resolution of all AEs to baseline or grade 1, dalantercept/placebo should be reduced two dose levels, or the patient should discontinue treatment. If a patient has a repeating AE or an AE of similar nature that would require a dose modification, the patient should be dose reduced to the next dose level or the patient should discontinue treatment depending upon the nature of the AE and the patient status. The rules for management of AEs described in [Table 3](#) are applicable to all scheduled visits as well as any unscheduled visits. Refer to [Table 4](#) and [Table 5](#), Dose Level Modifications, for dose level reductions.

Adverse events must resolve as outlined in [Table 3](#) prior to further dosing. For individual patients judged by the investigator to be at an unacceptable risk, despite not meeting the protocol-defined conditions for a dose modification, the investigator should consult with the medical monitor to decide whether to continue dosing at the same dose level, reduce the dose level, or discontinue the patient's treatment with dalantercept/placebo.

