**Table 3: Management of Adverse Events Related to Dalantercept/Placebo**

Adverse Event or Abnormal Finding	Action	Dalantercept Dose Modification
Weight/peripheral edema Eventsa - Weight gain (not due to fluid retention or edema) due to improvement in health would not be considered an adverse event or abnormal finding.		
1. $\geq 3$ to $< 5\%$ increase in weight from baseline or grade 1 peripheral edema	
 
● Administer therapya as needed to maintain approximate baseline weight or to reduce edema.
 
● Hold dalantercept/placebo treatment until weight returns to baseline (<math>< 3\%</math> increase) or edema resolves.
 
	1. Upon normalization of weight or resolution of edema, dalantercept/placebo should be restarted at the same dose level.
2. $\geq 5$ to $< 10\%$ increase in weight from baseline (Grade 1) or grade 2 peripheral edema		2. Upon normalization of weight or resolution of edema, dalantercept/placebo should be reduced one dose level.
3. $\geq 10\%$ increase in weight from baseline ( $\geq$ Grade 2) or grade 3 peripheral edema	
 
● Administer therapya as needed to maintain approximate baseline weight or to reduce edema.
 
● Hold dalantercept/placebo treatment until weight returns to baseline (<math>< 3\%</math> increase) or edema resolves.
 
● A complete cardiac evaluation including chest x-ray (CXR), ECG, ECHO, troponin, and BNP should be performed if determined to be clinically necessary.
 
	3. Upon normalization of weight or resolution of edema, dalantercept/placebo should be reduced two dose levels.
Pulmonary Events		
1. A new onset of signs or symptoms of pulmonary edema (Grade 1). Signs and symptoms include but are not limited to shortness of breath, coughing up blood, end-inspiratory crackles, etc.	
 
● Administer therapya as needed.
 
● Hold dalantercept/placebo treatment until resolution of AE(s).
 
● A complete cardiac evaluation including CXR, ECG, ECHO, troponin, and BNP should be performed if determined to be clinically necessary.
 
	1. Upon resolution of AE(s), dalantercept/placebo should be reduced one dose level.

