1. $\geq$ Grade 2 bleeding event with the exception of grade 2 epistaxis	
 
● Discontinue further dalantercept/placebo treatment.
 
	
2. Any other event $\geq$ Grade 3 [e.g., hyponatremia (< 130 mmol/L)] with the exception of $\geq$ Grade 3 amylase and/or lipase in the absence of clinical symptoms.	
 
● Hold dalantercept/placebo treatment until resolution of AE(s).
 
● Work up as appropriate (e.g., serum and urine osmolality, serum and urine sodium, etc.).
 
	
 
2. Upon resolution of AE(s) to grade 1 or baseline, dalantercept/placebo should be reduced one dose level.
 

a Investigators can administer fluid management therapy as described in [Section 10.6.3](#) (Fluid Management Therapy).

b Note that treatment with diuretics is expected for some patients during this study and should not be used to determine grading of hypertension.

Patients are allowed up to 3 dose modifications (Table 3) due to AEs (e.g., from 0.9 mg/kg to 0.68 mg/kg, from 0.68 mg/kg to 0.51 mg/kg, and from 0.51 mg/kg to 0.38 mg/kg).

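### For four fluid-event rows of Table 3, the restart condition for a patient with several dose-modifying adverse events does not match the table, and the protocol does not say which text governs

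*Combined protocol and SAP*

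**What the plan says.** Three pieces of text in the protocol bear on when dalantercept/placebo may be restarted.

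- **The several-event sentence (Section 10.6.1).** Its trigger is "If more than 1 AE occurs that would require a dose modification". Its consequence is "upon resolution of all AEs to baseline or grade 1, dalantercept/placebo should be reduced two dose levels", with stopping treatment as the alternative.
- **The general restart sentence (Section 10.6.1, next paragraph).** "Adverse events must resolve as outlined in" Table 3 before dosing continues. No exception is made for patients with several events. Just before it, the section says that the Table 3 rules hold at scheduled and unscheduled visits alike.
- **Table 3.** The row for "A new onset of signs or symptoms of pulmonary edema (Grade 1" has the action "Hold dalantercept/placebo treatment until resolution of AE(s", followed by a reduction of one level. Grade 2 or higher pulmonary edema has the same hold, then two levels. Weight gain of 5 to <10%, which the table itself labels Grade 1, or grade 2 peripheral edema, restarts one level lower when weight is normal or edema has resolved. Gain of 10% or more, or grade 3 edema, restarts two levels lower on the same condition. The table takes a gain below 3% as back to baseline.

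One further row matters. For any other event of grade 3 or higher, the action column says to hold until resolution, while the dose column says "Upon resolution of AE(s) to grade 1 or baseline, dalantercept/placebo should be reduced one dose level".

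**The concern.** The several-event sentence accepts residual grade 1 events at restart. For some fluid events Table 3 does not, and grade 1 pulmonary edema is in itself a reason to hold. A site that goes to the several-event sentence as the specific rule for its patient could redose at a point where Table 3 would still hold.

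The events concerned are central to this drug. Section 9.2.1 names fluid overload as the dose-limiting toxicity in Phase 1. Section 7.3 describes dose-dependent fluid retention showing as peripheral edema, dyspnea and weight gain, so it is plausible that two such events occur together.

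The choice of reading also affects who stays on treatment. A patient kept on hold moves toward the limit in Section 10.6.1: "If administration of dalantercept/placebo cannot be resumed within 3 weeks after the scheduled start of the next treatment cycle", the patient should leave the study, although exemptions may be considered where the investigator sees clinical benefit. In Part 2, stopping either drug ends study treatment (Synopsis; Section 9.1). Patients who stop without progression are censored for PFS at their last on-study tumor assessment (Section 15.4.1). Those who go on with axitinib alone need not return for three-monthly scans (Section 12.2.2). There is thus a path from an ambiguous restart rule to the primary endpoint.

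**Working it through.** No power, event count or significance level enters this point, so the check is a comparison of texts. Each fluid or effusion row of Table 3 is set against the several-event threshold of baseline or grade 1.

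| Table 3 row | Condition for dosing in Table 3 | Compared with baseline or grade 1 | Dose step in Table 3 |
|---|---|---|---|
| Gain 3 to <5%, or grade 1 peripheral edema | gain <3%, or edema resolved | stricter, but probably no trigger | none (same dose) |
| Gain 5 to <10% (labelled Grade 1), or grade 2 peripheral edema | weight normal, or edema resolved | **stricter** | one level |
| Gain ≥10%, or grade 3 peripheral edema | gain <3%, or edema resolved | **stricter** | two levels |
| Grade 1 pulmonary edema | resolved | **stricter** | one level |
| Grade ≥2 pulmonary edema | resolved | **stricter** | two levels |
| Grade 1 pleural effusion | no hold stated | looser | one level |
| Grade ≥2 pleural effusion | grade 1 or lower | equal | two levels |
| Grade 2 pericardial effusion | stable or resolved on repeat ECHO | looser | one level |

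The mismatch is therefore confined to the four rows in bold. The first row is set aside because the drug restarts at the same dose, and the text below Table 3 illustrates dose modifications only by reductions (0.9 to 0.68 to 0.51 to 0.38 mg/kg). The action cell for a gain of 5 to <10% is blank in the text as extracted and seems to be shared with the row above. The restart condition shown is the one in that row's dose column.

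**Example.** A Part 2 patient on 0.9 mg/kg has a related weight gain of 5 to <10% and related grade 1 pulmonary edema. Each calls for a reduction, so the several-event sentence is triggered.

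1. Several-event sentence alone: both events are grade 1 by the table's own labels, so the threshold is met at onset. The patient may be redosed two levels lower, which Table 5 gives as 0.9 → 0.68 → 0.51 mg/kg, or treatment stops.
2. Table 3: no dosing until the gain is below 3% and the pulmonary edema has resolved.
3. Dose step: either event alone costs one level (0.68 mg/kg). Together they cost two levels (0.51 mg/kg) or discontinuation. The step is heavier even where the restart point is earlier. For the two rows that already require two levels, the step is the same, with discontinuation added as an alternative.

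**Can the texts be read together?** Yes: Table 3 could set when dosing restarts, and the several-event sentence how far the dose drops. For the four rows, however, the words allowing grade 1 then do nothing.

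**Does the word resolution settle it?** No, because Table 3 uses it in two senses. For grade 2 or higher pleural effusion, the action column holds to grade 1 or lower and the dose column speaks only of resolution. In the row for other events of grade 3 or higher, the explicit grade 1 wording is in the dose column instead. If resolution always meant grade 1, the hold for grade 1 pulmonary edema would be satisfied the moment it began.

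**The case against.** The strongest reply is that Section 10.6.1 settles the matter itself. The general restart sentence has no exception, it follows the several-event sentence, and it points to Table 3. On that reading there is no early restart, and several events only bring a larger reduction. This is a coherent reading and may be the one intended. It does not remove the inconsistency: the several-event sentence still states its own restart condition, a site can treat that as the specific rule for its case, and no order of precedence is given.

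A reader might infer that two fluid events get a more lenient rule than one. The documents do not support that in general. It needs the several-event sentence to be read alone, it concerns only the restart threshold, and in no row is the dose step lighter. The pleural and pericardial effusion rows are equal or looser in Table 3.

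Other replies also carry weight.

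- The trigger is not certain. Section 10.6.1 has a separate sentence for a repeating event or one of similar nature, with reduction to the next level or discontinuation, and two signs of fluid retention might be placed there. That sentence states no restart threshold, so it adds to the ambiguity.
- The two columns of the row for other events of grade 3 or higher are loose wording more than opposing instructions, since the specific cell can be taken to qualify the general one.
- The 3-week limit is not absolute, given the exemptions.
- Events are reviewed before each dose, the investigator may delay for any event, and the DMC sees unblinded safety data. These limit the harm from a wrong reading, but do not tell sites which reading is right.

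**Conclusion.** The point stands as an internal inconsistency of moderate severity, limited to the four rows identified. Section 10.6.1 and Table 3 give different restart conditions for the same fluid events, and the protocol does not say which governs when several occur.

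The number of patients affected cannot be estimated from the documents. In the Phase 1 study, 3 of 37 patients (3/37 = 8.1%) had treatment-related serious events of fluid overload and/or heart failure. That was monotherapy at 0.1 to 4.8 mg/kg with no renal cell carcinoma patients. It shows that the risk exists, but not how often two lower-grade events coincide at 0.9 mg/kg with axitinib. The conflict also bites only where an event in one of the four rows is still at grade 1 when the restart decision is made.

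A reader might go on to infer a bias in the PFS comparison. The route through discontinuation and censoring exists in the text, but nothing in the documents shows its size or direction, so no effect on the primary analysis is claimed.

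The conclusion assumes that a dose modification means a reduction in dose level, as the protocol's examples suggest, and that two concurrent fluid events count as more than one event.

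**What to change.** In the next amendment, reconcile the several-event sentence and the general restart sentence of Section 10.6.1 with the four Table 3 rows, and state which text governs the restart decision when more than one event is present. Align the wording of the two columns in the row for other events of grade 3 or higher. Which threshold applies is a clinical decision for the sponsor's clinical team, and no view on it is offered here.

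The cost is one sentence in Section 10.6.1, one cell of Table 3 and a memo to sites. No procedures, visits or patients are added.

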**Table 3: Management of Adverse Events Related to Dalantercept/Placebo**

Adverse Event or Abnormal Finding	Action	Dalantercept Dose Modification
Weight/peripheral edema Eventsa - Weight gain (not due to fluid retention or edema) due to improvement in health would not be considered an adverse event or abnormal finding.		
1. $\geq 3$ to $< 5\%$ increase in weight from baseline or grade 1 peripheral edema	
 
● Administer therapya as needed to maintain approximate baseline weight or to reduce edema.
 
● Hold dalantercept/placebo treatment until weight returns to baseline (<math>< 3\%</math> increase) or edema resolves.
 
	1. Upon normalization of weight or resolution of edema, dalantercept/placebo should be restarted at the same dose level.
2. $\geq 5$ to $< 10\%$ increase in weight from baseline (Grade 1) or grade 2 peripheral edema		2. Upon normalization of weight or resolution of edema, dalantercept/placebo should be reduced one dose level.
3. $\geq 10\%$ increase in weight from baseline ( $\geq$ Grade 2) or grade 3 peripheral edema	
 
● Administer therapya as needed to maintain approximate baseline weight or to reduce edema.
 
● Hold dalantercept/placebo treatment until weight returns to baseline (<math>< 3\%</math> increase) or edema resolves.
 
● A complete cardiac evaluation including chest x-ray (CXR), ECG, ECHO, troponin, and BNP should be performed if determined to be clinically necessary.
 
	3. Upon normalization of weight or resolution of edema, dalantercept/placebo should be reduced two dose levels.
Pulmonary Events		
1. A new onset of signs or symptoms of pulmonary edema (Grade 1). Signs and symptoms include but are not limited to shortness of breath, coughing up blood, end-inspiratory crackles, etc.	
 
● Administer therapya as needed.
 
● Hold dalantercept/placebo treatment until resolution of AE(s).
 
● A complete cardiac evaluation including CXR, ECG, ECHO, troponin, and BNP should be performed if determined to be clinically necessary.
 
	1. Upon resolution of AE(s), dalantercept/placebo should be reduced one dose level.
2. $\geq$ Grade 2 pulmonary edema	
 
● Administer therapya as needed.
 
● Hold dalantercept/placebo treatment until resolution of AE(s).
 
● A complete cardiac evaluation including CXR, ECG, ECHO, troponin, and BNP should be performed if determined to be clinically necessary.
 
	2. Upon resolution of AE(s), dalantercept/placebo should be reduced two dose levels.
3. Grade 1 pleural effusion	
 
● Administer therapy as needed
 
	3. Reduce dalantercept/placebo one dose level
4. $\geq$ Grade 2 pleural effusion	
 
● Administer therapy as needed
 
● Hold dalantercept/placebo treatment until resolution of AE to <math>\leq</math> Grade 1
 
	4. Upon resolution of AE, dalantercept/placebo should be reduced two dose levels.

Adverse Event or Abnormal Finding	Action	Dalantercept Dose Modification
Cardiovascular Events		
1. Grade 2 ejection fraction decreased	
 
● Administer therapy as needed
 
● Hold dalantercept/placebo treatment until resolution of AE(s) or improvement of EF > 50%.
 
● A cardiac evaluation including ECHO should be performed prior to starting next cycle.
 
● Consider holding or modifying dose of axitinib.
 
	
 
1. Upon resolution of AE(s) or improvement of EF > 50% dalantercept/placebo should be reduced one dose level and continue to follow repeat ECHO every 6-12 weeks throughout study duration.
 
2. Consider axitinib dose modification if determined to be clinically necessary.
 

2. Grade 2 pericardial effusion detected on imaging	
 
● Administer therapy as needed
 
● Hold dalantercept/placebo treatment and repeat ECHO prior to starting next cycle. in three weeks
 
	
 
3. If stable or resolved on repeat ECHO, reduce dalantercept/placebo one dose level. Repeat ECHO as clinically indicated. If worsened, discontinue dalantercept/placebo.
 

3. $\geq$ Grade 3 cardiovascular event b including grade 3 pericardial effusion detected on ECHO	
 
● Discontinue further dalantercept/placebo treatment.
 
	
Other Events		
1. $\geq$ Grade 2 bleeding event with the exception of grade 2 epistaxis	
 
● Discontinue further dalantercept/placebo treatment.
 
	
2. Any other event $\geq$ Grade 3 [e.g., hyponatremia (< 130 mmol/L)] with the exception of $\geq$ Grade 3 amylase and/or lipase in the absence of clinical symptoms.	
 
● Hold dalantercept/placebo treatment until resolution of AE(s).
 
● Work up as appropriate (e.g., serum and urine osmolality, serum and urine sodium, etc.).
 
	
 
2. Upon resolution of AE(s) to grade 1 or baseline, dalantercept/placebo should be reduced one dose level.
 

a Investigators can administer fluid management therapy as described in [Section 10.6.3](#) (Fluid Management Therapy).

b Note that treatment with diuretics is expected for some patients during this study and should not be used to determine grading of hypertension.

Patients are allowed up to 3 dose modifications (Table 3) due to AEs (e.g., from 0.9 mg/kg to 0.68 mg/kg, from 0.68 mg/kg to 0.51 mg/kg, and from 0.51 mg/kg to 0.38 mg/kg).

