#### **9.4. Patient Withdrawal Criteria**

Patients will be informed that they have the right to withdraw from study treatment or from the study at any time for any reason without prejudice to their medical care.

Patients may be withdrawn from study treatment for any of the following reasons:

- Patient's request
- Patient's unwillingness or inability to comply with the protocol
- Pregnancy
- Progression of disease

- Use of prohibited medications
- Medical reason, at the discretion of the investigator and/or the medical monitor
- At the discretion of the sponsor (i.e. discontinuation of the study)

Patients may be withdrawn from the study for any of the following reasons:

- Death
- Lost to follow-up
- Withdrawal of consent
- At the discretion of the sponsor (i.e. discontinuation of the study)

The reasons for withdrawal must be recorded in the patient's CRF. The investigator must notify the sponsor, the medical monitor and the contract research organization (CRO) when a patient has been discontinued/withdrawn due to an Adverse Event (AE).

The investigator must notify the sponsor and the CRO when a patient has been discontinued/withdrawn for reasons unrelated to the study or study drug (i.e., withdrawn consent, lost to follow up).

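### After a severe allergic reaction to dalantercept/placebo, Table 3's written default is to resume one dose level lower; nothing in the protocol requires a stop

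*Combined protocol and SAP*

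**What the plan says.** Section 10.6.1, Table 3, groups related events into weight and edema, pulmonary, cardiovascular and other. No row names allergy, anaphylaxis or hypersensitivity. The second row under Other Events takes in every remaining event of grade 3 or higher, exempting only raised amylase or lipase without symptoms. Its action is to hold treatment until the event resolves, and then: "Upon resolution of AE(s) to grade 1 or baseline, dalantercept/placebo should be reduced one dose level". Table 5 gives the Part 2 levels as 0.9, 0.68, 0.51 and 0.38 mg/kg, then discontinuation.

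Two categories carry a mandatory stop whatever the investigator thinks. For cardiovascular events of grade 3 or higher the instruction is "Discontinue further dalantercept/placebo treatment". The same instruction applies to bleeding at or above the threshold in the first Other Events row, "Grade 2 bleeding event with the exception of grade 2 epistaxis".

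The text around the table leaves room for judgment:

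- Patients with related events "may continue treatment with dalantercept/placebo, provided that the AE can be managed".
- "For any AE, including AEs not specifically mentioned in the table below, the investigator may decide to delay dosing or modify the dose level".
- After a repeat event, "the patient should be dose reduced to the next dose level or the patient should discontinue treatment depending upon the nature of the AE" and on the patient's status.
- Section 9.4 lists among the permitted reasons for withdrawal: "Medical reason, at the discretion of the investigator and/or the medical monitor".
- The synopsis ends dosing at progression or at toxicity that cannot be managed.

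**The concern.** Re-exposure to a protein that has just caused a severe allergic reaction is a decision most protocols take out of individual hands. Here the row that applies points toward re-dosing, and stopping depends on someone choosing to depart from it.

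The row was evidently not written with this event in mind. Its example is hyponatremia and its suggested work-up is osmolality and sodium. It asks for no allergy work-up and no anti-drug antibody result before the next dose. The protocol samples anti-drug antibodies on a schedule but links no result to dosing.

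The risk was foreseen. Section 7.4 mentions hypersensitivity twice, once as a toxicity seen with other anti-angiogenic agents and once as a possible consequence of anti-drug antibodies. Exclusion criterion 21 in Section 9.3.2 bars anyone with a past severe reaction (grade 3 or higher) to recombinant proteins or the excipients. A patient who has such a reaction to dalantercept on study would fail that criterion, yet the on-treatment default is to dose again. What is at stake is patient safety, not the validity of the primary analysis.

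**Working it through.** The protocol gives no figure to reproduce on this point, so the main check is to trace the event through the text.

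**Which rule applies**

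1. Weight/edema, pulmonary and bleeding rows: not applicable to an allergic reaction.
2. Cardiovascular row: applies only if the reaction is recorded as a cardiovascular event of grade 3 or higher (severe hypotension, for example). Treatment must then stop.
3. Otherwise the catch-all row applies: hold, then resume one level lower.

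**Does any other clause force a stop?**

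| Clause | Effect on this event |
|---|---|
| Continuation if the event can be managed (10.6.1); dosing until toxicity is unmanageable (synopsis) | Neither term is defined or tied to hypersensitivity |
| Investigator latitude for any event (10.6.1) | Permissive |
| Unacceptable-risk sentence (10.6.1) | Covers patients judged at risk "despite not meeting the protocol-defined conditions for a dose modification"; this patient does meet one |
| More than one event needing modification (10.6.1) | Two-level reduction or discontinuation |
| Repeat event (10.6.1) | Reduction or discontinuation, depending on the event and the patient |
| Three-week delay limit (10.6.1) | Not reached if the reaction resolves in time; exemptions possible |
| Withdrawal for a medical reason (9.4) | Permissive |
| Dose-limiting toxicity rules (10.7) | Govern Part 1 escalation and enrollment; patients in a cohort that stops escalation may continue dosing |

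No clause requires a stop for a single severe allergic reaction, and even a second one leaves reduction as a written option.

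**Dose on re-exposure (Table 5)**

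- First reduction: 0.68 / 0.9 = 0.756, about 76% of the starting dose.
- Second: 0.51 / 0.9 = 0.567, about 57%.
- Third: 0.38 / 0.9 = 0.422, about 42%.

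The second and third levels would matter only if reactions recurred and reduction were chosen each time.

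**How often it might happen**

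Section 7.3 reports treatment-related serious events in 5 of 37 Phase 1 patients: 3 with fluid overload and/or heart failure, 1 with left ventricular dysfunction and 1 with fatigue (3 + 1 + 1 = 5). That leaves 0 of 37 with hypersensitivity.

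- Exact one-sided 95% upper bound: 1 − 0.05^(1/37) = 0.0778, or 7.8%.
- Applied to 65 dalantercept patients: 65 × 0.0778 = 5.06.

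This is the most that zero events in 37 patients can exclude; it is not a forecast. Phase 1 was monotherapy, the data were preliminary, and a serious event is not the same as a grade 3 event.

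**Effect of a mandatory stop on the primary analysis**

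Section 15.2 triggers the analysis at 82 or more PFS events, so a censored patient delays it and does not reduce the event count. With monthly hazards ln 2 / 8 = 0.0866 and ln 2 / 5 = 0.1386 from the planning medians, accrual complete, and a 30.4-day month:

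| At risk | Events per month | Days per extra event |
|---|---|---|
| 48 (130 − 82, no dropout) | 4.16 to 6.65 | 7.3 to 4.6 |
| 24 (assumed heavy dropout) | 2.08 to 3.33 | 14.6 to 9.1 |

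Each lost event therefore costs about 5 to 15 days. The figure of 24 at risk is an assumption; the protocol does not give one.

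**The case against.** The best defense is that Section 10.6.1 allows continuation only when the event can be managed. Read that way, the catch-all row sets the dose for patients already cleared to resume and does not direct a re-challenge. A careful investigator would stop after anaphylaxis and has explicit authority to do so. After a repeat, the nature of the event is a stated criterion, and a reaction recorded as several events would draw a two-level cut or discontinuation. Patients are observed for 30 minutes after each dose (Section 10.5), adverse events are reviewed before the next dose (Section 12.2), serious events are notified within 24 hours (Section 14.7), and the DMC sees unblinded safety data (Section 10.7). The mandatory-stop rows match toxicity seen in Phase 1 or expected from the mechanism, while hypersensitivity is raised only generically and Section 7.4 says it is unknown whether dalantercept causes it.

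Much of this stands. Re-dosing is a default and not inevitable, the event is expected to be very rare, and the contrast with the bleeding and cardiovascular rows does not show inconsistency by itself. But every clause cited permits a stop without requiring one, and the oversight steps are not stopping rules. The Investigator's Brochure, Study Reference Guide and DMC charter were not available, so the finding covers this protocol only.

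**Conclusion.** The concern holds. For a related allergic or anaphylactic reaction of grade 3 or higher that is not recorded as cardiovascular, the stated rule is hold and then resume at 76% of the starting dose in Part 2, and the protocol nowhere requires discontinuation. Followed as written, it re-exposes a patient who would no longer meet the trial's own entry criteria. The expected number of such patients is near zero, with 7.8% as the upper limit that the Phase 1 serious-event data support. That makes it a modest point in frequency but a serious one for any patient affected, and it merits correction because the remedy is so small.

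**What to change.** In the catch-all row of Table 3, add to the exceptions allergic, anaphylactic or hypersensitivity reactions of grade 3 or higher that are possibly or probably related to dalantercept/placebo. Add a separate row for those events with the table's existing instruction: "Discontinue further dalantercept/placebo treatment".

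This takes one exception and one row in a protocol amendment, with no extra patients, visits or analyses. The price falls on the rare patient who might have tolerated re-dosing. Possible relatedness is a low bar (Section 14.4), so that patient could be on placebo or reacting to something else. In Part 2, stopping dalantercept/placebo also ends study treatment with axitinib (Section 9.1), and the patient may be censored for PFS (Section 15.4.1), with the short delay to the analysis worked out above.
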